1.1.3 Overview of Clinical Studies

In addition to Study ARN-509-003, apalutamide is also being evaluated in Phase I studies in healthy men and Phase I/II, Phase II, and Phase III studies in patients with prostate cancer.

Study ARN-509-001 is an ongoing Phase I/II study in patients with progressive advanced CRPC. In the Phase I portion of the study, 30 patients with mCRPC received at least 1 dose of apalutamide at escalating dose levels: 3 patients each at 30, 60, 90, 120, 180, 240, 390, 480 mg/day, and 6 patients at 300 mg/day. Three subgroups are being evaluated in the Phase 2 portion (Group 1: NM-CRPC; Group 2: mCRPC without previous ketoconazole, abiraterone acetate, enzalutamide or chemotherapy [for mCRPC]; and Group 3: mCRPC post abiraterone acetate, no previous chemotherapy [for mCRPC]). All patients received apalutamide orally once daily, except those in the 300, 390, and 480 mg cohorts who received a twice-daily dosing regimen due to the higher pill burden at those levels. The results of the Phase 1 portion of the study from 30 patients with mCRPC demonstrated that treatment with apalutamide resulted in PSA declines at all dose levels tested. Eighteen subjects (60%) had a ≥50% or higher maximum decrease in PSA from baseline and 6 (20%) had ≥90% maximum decrease. Ten patients had measurable soft tissue disease at baseline; 5 (50%) subjects maintained stable disease response for more than 6 months, 1 (10%) subject experienced disease progression, and the remaining 4 subjects had indeterminate responses. Apalutamide was well tolerated, with only 1 dose-limiting toxicity (DLT) at the 300 mg dose level (Grade 3 treatment-related abdominal pain). The event lasted 6 days and resolved with dose interruption and subsequent dose reduction to 240 mg (120 mg twice daily). Three additional subjects were treated at the 300 mg dose level with no reported DLTs. No seizures were reported at any dose level. The maximum tolerated dose (MTD) was not determined. The PK profile is linear and dose-proportional.

Sixteen subjects participated in an evaluation of AR binding in vivo using

16 β -[18F] fluor- α -dihydrotestosterone (FDHT) positron emission tomography (PET)/CT scan. Apalutamide treatment reduced FDHT uptake across all dose levels (30 to 390 mg dose levels). A plateau was reached at approximately 120 mg (with FDHT uptake near background) indicating saturation of AR binding. The mean plasma trough levels associated with this dose (2.5 µg/mL) were at the lower end of the range that produced tumor regression in the LNCaP/AR mouse model. Steady state plasma levels at the 240 mg dose level (3 to 6 µg/mL) were more in the range sufficient to elicit a tumor response in the mouse xenograft model. Therefore, the 240 mg daily regimen was chosen for Phase 2 and Phase 3 dosing.

Apalutamide was rapidly absorbed, with measurable plasma concentrations within 30 minutes after ingestion of a single oral dose of 1 to 16 soft gelatin capsules (total apalutamide dose, 30 to 480 mg). On average, peak plasma concentrations occurred 2 to 3 hours after administration in each dose group. The increases in plasma C_{max} values and in the area under the plasma concentration curve (AUC) were linear and dose proportional. Plasma apalutamide concentrations declined slowly, with a mean half-life value at steady-state of 4 days.

The percentage of patients with PSA reductions of $\geq 50\%$ at 12 weeks in patients with NM-CRPC was 89%². Similar data were observed after 24 weeks. The data available to date indicate that apalutamide shows durable PSA responses in NM-CRPC and early mCRPC (before treatment with abiraterone acetate or chemotherapy). Apalutamide also has activity in a subgroup of patients with mCRPC that have progressed on abiraterone acetate. For the NM-CRPC subgroup, the median time to PSA progression was 24.0 months (16.3 – NR).

In the NM-CRPC subgroup (n =51), the most frequent treatment-related adverse events reported in >10% are fatigue (61%), diarrhea (43%), and nausea (39%)². No deaths were reported in this subgroup as of the safety cutoff.

In the phase 3 study, the median metastasis-free survival with apalutamide versus placebo was (40.5 vs. 16.2 months, p < 0.001).³

1.2 STEREOTACTIC BODY RADIATION THERAPY IN OLIGOMETASTATIC PROSTATE CANCER

The definition of oligometastatic prostate cancer has varied across studies. Multiple uncontrolled and prospective studies had defined as ranging from ≤ 3 to ≤ 5 lesions in various studies²¹. A recent retrospective analysis of pooled individual data from patients with castration-sensitive recurrent prostate cancer following definitive local therapy, with up to three positive lesions on baseline scan, to determine the efficacy of this treatment strategy. SBRT was defined as a radiotherapy dose of at least 5 Gy per fraction to a biologically effective dose (BED) of at least 80 Gy. A total of 119 patients were treated for 163 metastatic lesions (lymph node, n = 72; bone n = 43; visceral met n = 2). The 3-year and 5-year local progression free survival rate was 93% and 92%, respectively. A lower radiotherapy dose predicted for higher local recurrence rate. The median distant progression-free survival time was 21 months (95% CI 15-27 months)¹⁹. A recent review highlighted 5 additional retrospective studies demonstrates the safety of SBRT to oligometastatic sites of disease, as well as the high rates of local control ranging from 90-100%²⁰.

Two major limitations of the currently available data are randomized studies with and without SBRT to begin to address whether addition of SBRT impacts intermediate- and long-term outcomes, as well as limited data available in the oligometastatic castration-resistant prostate cancer setting. The current study was designed to address these gaps and evaluate the role of SBRT in oligometastatic CRPC in a randomized fashion, with treatment of up to five bone and nodal radiation fields.

2 STUDY OBJECTIVES

2.1 PRIMARY OBJECTIVE

To demonstrate whether the proportion of patients with an undetectable serum PSA at 6 months following cessation of apalutamide is higher with addition of SBRT to PSMA-avid oligometastatic sites of disease compared to the group of patients receiving apalutamide monotherapy.

2.2 SECONDARY OBJECTIVES

1. To compare the time to PSA progression by PCWG criteria between treatment arms
2. To evaluate the safety and tolerability of apalutamide in combination with SBRT.

2.3 EXPLORATORY OBJECTIVES

1. *To evaluate the genomic factors associated with the presence of oligometastatic disease via exome sequencing.*
2. *To evaluate the association between somatic and germline genomic alterations including but not limited to AR amplification and point mutations and alterations in DNA damage response pathway with outcomes on protocol therapy*

Note: The italicized objectives above were discontinued in Protocol v. 8.0. See [Section 7.3](#) for additional information.

3. To characterize the metastatic pattern at baseline and at progression in these patients and to determine whether features of the baseline PSMA-PET scan are associated with treatment outcomes.

3 STUDY DESIGN

3.1 STUDY OVERVIEW AND RATIONALE

This is a randomized, open-label, phase II clinical trial evaluating the efficacy and safety of apalutamide with or without SBRT in patients with oligometastatic castration-resistant prostate cancer detected on PSMA-PET scan imaging. A randomized design was chosen to begin to address the clinically relevant question as to whether the addition of SBRT improves outcomes as compared to systemic therapy alone for men with oligometastatic prostate cancer. We chose to utilize PSMA-PET as opposed to conventional imaging to define oligometastatic disease based on the improved sensitivity of this imaging modality, enabling earlier detection of oligometastatic disease.

The justification of assigned therapy by treatment arm is as follows:

(1) SBRT: There is no standard timing for the use of SBRT for patients with oligometastatic disease. Therefore, it is appropriate to undertake SBRT either at the time of starting apalutamide as part of study treatment, or later, as post-study therapy. We chose to utilize SBRT as compared to more conventional radiation treatment schedule due to the higher rates of local control observed with higher doses of radiation therapy in prior studies of radiation in oligometastatic prostate cancer.

(2) Apalutamide therapy: Apalutamide is not considered SOC therapy in this group of patients, and consequently will be provided by the study. Apalutamide is being used in both arms of the study in order to maintain equipoise with regards to PSA endpoints. The optimal duration of concurrent androgen pathway inhibitor treatment in conjunction with ADT remains undefined. The SPARTAN study has studied maintenance of apalutamide therapy until radiographic disease progression, and not for a fixed time period as in this study.

However the optimal duration of apalutamide therapy in this setting has not been determined. Extrapolation from other studies evaluating the use of AR targeted therapy in hormone-naïve prostate cancer patients with recurrent, but non-extensive disease suggests that the approach selected is appropriate. Clinical trials testing AR targeted therapy in conjunction with “salvage” radiotherapy in men with progressive disease following prostatectomy have utilized AR targeted therapy from 6 months (Carrie et al, Lancet Oncol 2016) to 24 months (Shipley et al, NEJM, 2017.) Furthermore, in a trial of intermittent androgen deprivation in patients with non-metastatic disease progression following radiation therapy, one year of systemic therapy was used (Crook et al, NEJM, 2012). One year of apalutamide therapy will therefore be used in both arms. Shorter duration is felt inadequate for patients with potentially metastatic disease, whereas longer duration would delay read out of results.

Although SBRT is an appropriate therapeutic approach in selected patients with oligometastatic prostate cancer, its utility has not been rigorously demonstrated. It is hypothesized that the addition of SBRT to apalutamide will result in clinically meaningful benefit, with improvement in time to subsequent metastasis, and potentially in an overall survival benefit. However, before embarking on a large phase 3 trial, an intermediate signal of activity is required. Only a very small proportion (2.5%) of patients with non-metastatic CRPC treated with apalutamide alone reach a serum PSA level of < 0.2 ng/mL. A nadir PSA of < 0.2 ng/mL has previously been shown to be strongly associated with long-term survival, and therefore represents a reasonable intermediate endpoint for a randomized phase 2 study. Positive results from the current study would form the strong justification for a follow-on randomized phase 3 study to investigate whether addition of SBRT impacts long-term treatment outcomes including radiographic progression-free and overall survival.

3.1.1 Number of Subjects

A total of 60 subjects may participate in this study. Thirty subjects will be enrolled to the apalutamide monotherapy arm, and 30 patients will be enrolled to the apalutamide + SBRT arm.

3.2 STUDY OUTCOMES

3.2.1 Primary Endpoints

Proportion of patients with undetectable serum PSA (< 0.2 ng/mL) at 6 months following completion of apalutamide therapy (18 months from date of randomization).

3.2.2 Secondary Endpoints

1. Time to PSA progression by PCWG criteria
2. Feasibility and safety of apalutamide and concurrent SBRT

3.2.3 Exploratory Endpoints

1. *Association between genomic factors and presence of oligometastatic disease*
2. *Association between somatic and germline genomic alterations with clinical outcomes*

Note: The italicized objectives above were discontinued in Protocol v. 8.0. See [Section 7.3](#) for additional information.

3. Association between baseline PSMA-PET scan uptake and distribution of lesions with treatment outcomes.

4 PATIENT SELECTION

The following eligibility criteria are designed to select patients for whom protocol treatment is considered appropriate. All relevant medical and non-medical conditions should be taken into consideration when deciding whether this protocol is suitable for a particular patient. It is expected that all patients will be treated according to local standard of care, including radiation therapy if needed for local disease, prior to enrolling.

No waivers will be granted for eligibility criteria deviations.

Patients considered screen failures may be subsequently rescreened. Rescreening must be discussed with and approved by the Principal Investigator on a case-by-case basis. Patients who are determined to be eligible for the study after rescreening must sign a new informed consent form (ICF) and be assigned a new patient number.

4.1 INCLUSION CRITERIA

1. Histologically or cytologically confirmed adenocarcinoma of the prostate.
2. Progressive, castration-resistant prostate cancer demonstrated during continuous ADT, defined as 3 PSA rises at least 1 week apart, with a minimum PSA > 0.2 ng/mL obtained during Screening.
3. At least one but no more than 5 discrete PSMA-avid radiation fields on baseline PSMA-PET scan. All PSMA-avid lesions in radiation fields must be amenable to SBRT in judgment of treating radiation oncologist. There are no restrictions on site of lesion/radiation field (e.g. bone, lymph node, prostate, visceral). Equivocal lesions/radiation fields on PSMA PET scan that are not definitive for metastasis will not count towards the limit of 5 radiation fields and will not undergo SBRT.
4. Surgically or medically castrated, with testosterone levels of <50 ng/dL during Screening. If the patient is medically castrated, continuous dosing with LHRH analogue must have been initiated at least 4 weeks prior to randomization and must be continued throughout the study to maintain castrate levels of testosterone including post-treatment follow up period.
5. No prior systemic treatment initiated for the treatment of castration resistant prostate cancer, including abiraterone acetate, enzalutamide, apalutamide, darolutamide, other novel AR or CYP17 antagonist, or docetaxel.
6. Patients receiving bone loss prevention treatment with bone-modifying agents (e.g. denosumab, zoledronic acid) must be on stable doses for at least 4 weeks prior to randomization
7. Patients who received a first generation anti-androgen (e.g., bicalutamide, flutamide, nilutamide) as most recent treatment must have at least a 6-week washout prior to randomization and must show continuing disease (PSA) progression (an increase in PSA) after washout.
8. At least 4 weeks or 5 half-lives, whichever is shorter, must have elapsed from the use of any anti-cancer therapy, other than LHRH analog or first generation antiandrogen, prior to randomization
9. At least 4 weeks must have elapsed from major surgery or radiation therapy prior to randomization
10. Age \geq 18 years

11. Eastern Cooperative Oncology Group (ECOG) Performance Status grade 0 or 1
12. Resolution of all acute toxic effects of prior therapy or surgical procedure to Grade 1 or baseline prior to randomization
13. Adequate organ function as defined by the following criteria:
 - a. Serum aspartate transaminase (AST; serum glutamic oxaloacetic transaminase [SGOT]) and serum alanine transaminase (ALT; serum glutamic pyruvic transaminase [SGPT]) $\leq 2.5 \times$ upper limit of normal (ULN)
 - b. Total serum bilirubin $\leq 1.5 \times$ ULN. In subjects with known or suspected Gilbert's syndrome, if total bilirubin is $>1.5 \times$ ULN, direct bilirubin is $\leq 1.5 \times$ ULN
 - c. Glomerular filtration rate ≥ 45 ml/min based on Cockcroft-Gault equation
 - d. Absolute neutrophil count (ANC) $\geq 1500/\text{microliter}$
 - e. Platelets $\geq 75,000/\text{microliter}$
 - f. Hemoglobin $\geq 9.0 \text{ g/dL}$
 - g. Serum albumin $\geq 3.0 \text{ g/dL}$
14. Signed and dated informed consent document indicating that the patient has been informed of all pertinent aspects of the trial prior to randomization.
15. Willingness and ability to comply with scheduled visits, treatment plans, laboratory and radiographic assessments, and other study procedures, including ability to swallow study drug tablets and long-term follow-up.
16. Agrees to use a condom (even men with vasectomies) and another effective method of birth control if he is having sex with a woman of childbearing potential or agrees to use a condom if he is having sex with a woman who is pregnant while on study drug and for 3 months following the last dose of study drug. Must also agree not to donate sperm during the study and for 3 months after receiving the last dose of study drug.

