4.5 RANDOMIZATION PROCEDURES

Once eligibility is confirmed, subjects will be randomized with equal probability to 1 of the 2 treatment arms. Balance in treatment assignment will be achieved using a randomized block design. Randomization will be carried out via computer generated random assignment. All subjects must commence treatment within 7 calendar days after randomization. Study sites will email the Eligibility Checklist to the Lead site (UCSF) in order to obtain the subject's treatment assignment. Once subject eligibility is confirmed by the lead site, an email with the treatment assignment number will be provided to the study site.

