12.2 ANALYTIC PLAN

12.2.1 Analysis of Primary Endpoint

The primary endpoint for the study is the proportion of patients with undetectable serum PSA (< 0.2 ng/mL) at 6 months following completion of apalutamide therapy (18 months from date of randomization). Fisher's exact test will be used to compare the proportion in the two treatment arms. Patients who discontinue apalutamide prior to completion of 12 months of therapy for reasons other than disease progression by PCWG criteria, as well as patients who withdraw or are lost to follow up, will be considered inevaluable for this analysis. Patients who discontinue treatment for radiographic or clinical progression, even if occurring prior to receipt of SBRT in the experimental arm), would be evaluable for analysis of the primary endpoint.

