12.2.5 Determination of Sample Size

The sample size is based upon the primary endpoint of the study, the proportion of patients with an undetectable serum PSA (< 0.2 ng/mL) 6 months following completion of protocol therapy with apalutamide. Assuming a 10% inevaluable/drop-out rate per treatment arm, a sample size of 60 patients (30 patients/arm) provides 84% power to detect a difference in proportion of patients with undetectable PSA of 25% in the apalutamide + SBRT arm vs. 2.5 % in the apalutamide without SBRT treatment arm, with a unidirectional level of significance of 0.10 using Fisher's exact test.

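### Entry PSA probably predicts the PSA < 0.2 ng/mL endpoint strongly, yet neither the randomisation nor the primary test uses it, and power is stated only at a 2.5% control rate

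*Combined protocol and SAP*

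**What the plan says.** Inclusion criterion 2 (section 4.1) sets the PSA requirement: "defined as 3 PSA rises at least 1 week apart, with a minimum PSA > 0.2 ng/mL obtained during Screening". No higher minimum is given.

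The primary endpoint (sections 3.2.1 and 12.2.1) is "undetectable serum PSA (< 0.2 ng/mL) at 6 months following completion of apalutamide therapy (18 months from date of randomization").

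Section 4.5 describes allocation: "Balance in treatment assignment will be achieved using a randomized block design". No stratification factor is named there or in section 5.1. Section 12.2.1 gives the primary test: "Fisher's exact test will be used to compare the proportion in the two treatment arms". It has no covariate or stratum. Section 12.2.2 says the Cox model for time to PSA progression will use factors listed earlier, but none are listed, so entry PSA is not named for that analysis either.

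Section 12.2.5 says that 30 men per arm, with 10% inevaluable, "provides 84% power to detect a difference in proportion of patients with undetectable PSA of 25% in the apalutamide + SBRT arm vs. 2.5" percent on apalutamide alone, "with a unidirectional level of significance of 0.10 using Fisher's exact test". The support for the control rate is in section 3.1: "Only a very small proportion (2.5%) of patients with non-metastatic CRPC treated with apalutamide alone reach a serum PSA level of < 0.2 ng/mL". No baseline PSA is given for that group, and none is projected for this trial.

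**The concern.** The entry floor and the success threshold are the same number. A man entering at 0.21 ng/mL needs a fall of about 5% to be below 0.2 (0.01/0.21 = 4.8%). A man entering at 10 ng/mL needs a fall of 98% (1 − 0.2/10). A baseline value that sets the required fall so directly is likely to be one of the strongest predictors of the outcome, and it is already measured at screening.

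Two things are at stake. First, an unstratified test on about 27 men per arm gives away power if success rates differ widely by entry PSA, and an uneven split of low-PSA men can move the result in either direction. Second, the whole power statement rests on one control rate. That rate comes from a population whose entry PSA is not described, so a reader cannot judge how far it carries over to men enrolled down to 0.2 ng/mL.

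**Working it through.** **Inputs from the documents.** 30 per arm with 10% inevaluable, so 30 × 0.9 = 27 evaluable per arm; 25% vs 2.5%; one-sided 0.10; Fisher's exact test (all section 12.2.5). Entry PSA > 0.2 (4.1); success < 0.2 at month 18 (12.2.1). On apalutamide, 89% of men with non-metastatic CRPC had a PSA fall of at least 50% at 12 weeks (1.1.3).

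**Step 1: reproduce the stated power.** Let X ~ Bin(27, p_C) and Y ~ Bin(27, p_T). Reject when the hypergeometric tail P(Y' ≥ y | x + y) ≤ 0.10, and sum the joint binomial probabilities over the rejection region. With p_C = 0.025 and p_T = 0.25 this gives 83.6%, which matches 84%. The arithmetic of the plan is sound.

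**Step 2: vary the control rate (an assumption; the documents give no range).**

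| Control rate | Power, SBRT arm held at 25% | Power, 22.5-point gain held |
|---|---|---|
| 1% | 90.2% | 87.1% |
| 2.5% | 83.6% | 83.6% |
| 5% | 70.4% | 77.6% |
| 10% | 44.0% | 67.8% |

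The first power column is a worst case for control rates above 2.5%, because low-PSA men would enter both arms and not only the control arm.

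**Step 3: can the direction be settled?** Suppose PSA falls by a fraction q on drug and then doubles every d months for 6 months off drug. The largest entry PSA still below 0.2 at month 18 is 0.2 / [(1 − q) × 2^(6/d)].

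| Assumed fall q | d = 3 months | d = 6 months | d = 10 months |
|---|---|---|---|
| 90% | 0.50 | 1.00 | 1.32 |
| 50% | 0.10 | 0.20 | 0.26 |

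With a 90% fall, men entering at up to 0.5–1.3 ng/mL could succeed without SBRT. With a 50% fall, no eligible man could at d = 3 or 6 months. The doubling times are assumptions. The documents support the 50% fall in most non-metastatic men; their only 90% figure is a maximum decrease in 6 of 30 phase 1 metastatic patients (20%). The direction is therefore not settled.

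**Step 4: sensitivity to a few men.** At 27 per arm, significance needs 4 SBRT successes if the control arm has 0, 5 if it has 1, 7 if it has 2, and 8 if it has 3. If 20% of men were low-PSA (assumption), two arms of 30 would differ by 4 or more such men about 26% of the time.

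**Step 5: false positives.** With equal rates in both arms, Fisher's exact size is 0.2% at a rate of 2.5%, 4.3% at 10%, and at most about 5.3% for the rates from 2.5% to 25% that were examined. It stays below 0.10.

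**Step 6: what stratifying the test buys.** The exact conditional test fixes the number of successes in each PSA stratum and takes the upper tail of the sum of two independent hypergeometric counts. Simulated power at 27 per arm with unstratified allocation (20,000 runs; all shares and rates are assumptions):

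| Low-PSA share | Low-PSA success, control vs SBRT | Other men, control vs SBRT | Fisher | Stratified exact |
|---|---|---|---|---|
| 20% | 40% vs 60% | 0% vs 20% | 64% | 70% |
| 20% | 50% vs 70% | 1% vs 25% | 68% | 78% |
| 20% | 50% vs 50% | 2.5% vs 25% | 51% | 56% |
| 10% | 50% vs 50% | 2.5% vs 25% | 66% | 69% |
| PSA not prognostic | 2.5% vs 25% | 2.5% vs 25% | 84% | 81.5% |

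In the second row, separate simulations gave gains from 8 to 11 points. In the null scenarios run, the size of the stratified test was between 2.6% and 4.5%.

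**The case against.** A reader might infer that low-PSA entrants push the control rate above 2.5%. The documents do not support that. The 2.5% is the share who ever reach < 0.2 on apalutamide, whereas the endpoint is read six months after stopping, in men whose PSA was rising on castration therapy. That pulls the rate down. Entry also requires a PSMA-avid lesion, so the PSA floor is not the only filter. This part of the objection stands: the net direction is unknown.

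A reader might also infer that the trial could not tell an SBRT effect from a low starting PSA. That is wrong. Randomisation balances entry PSA in expectation, chance imbalance is already inside Fisher's error rate, and the size stays below 0.10. There is no bias and no false-positive problem.

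The remaining objections concern size. The 44% figure is a worst case. The gain from stratifying is modest, and smallest where low-PSA men get no SBRT benefit. No cut such as 1.0 ng/mL has a basis in the documents. Changing the primary test in an open-label trial that has already reached protocol version 8.0 can cost credibility. All of this is fair. It governs how and when the change is made, but it does not remove the case for using a predictive baseline value that is already collected.

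**Conclusion.** The point holds as one of efficiency and transparency. Entry PSA is likely to be strongly prognostic because the floor equals the success threshold, and the plan uses it neither in allocation nor in the primary comparison. That it is prognostic is an inference from the threshold arithmetic; the documents report no data on it.

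The 84% is correct arithmetic for one control rate that is not tied to this population. Plausible departures move power from about 90% (control 1%, SBRT 25%) to 70–78% (control 5%) or 44–68% (control 10%). Adjusting for entry PSA recovers roughly 4 to 10 points under the assumed scenarios and loses about 2 if entry PSA is not prognostic. The low-PSA share and the stratum success rates behind those gains are assumptions. This is a worthwhile improvement and not a flaw that invalidates the comparison.

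**What to change.** **Section 12.2.1.** Before any comparison of outcomes by arm, prespecify as the primary test a one-sided 0.10 exact conditional test stratified by screening PSA. Fix the cut in advance, for example 1.0 ng/mL or the pooled median computed without reference to arm, and state that it is an assumption. Report success rates by arm within each stratum.

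**Section 4.5.** If accrual still allows, stratify the block randomisation on the same cut. If not, use the stratified test alone.

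**Section 12.2.5.** State that 84% power holds only at a 2.5% control rate, and show the range in the table above. Say what is known about baseline PSA in the source population and what is expected here.

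**Cost.** Changes to analysis wording and, if used, two block lists in place of one. No new data are needed, and eligibility, treatment and visits do not change. The statistical downside is about 2 points of power (84% to 81.5%) if entry PSA is not prognostic. The amendment should record its date and that no outcome comparison by arm had been made.
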